Mahdy et al., noted that SASI has the following advantages over other bariatric procedures: SASI has a shorter operative time compared to other procedures; 2) easy access to the duodenum and biliary tree endoscopically; 3) SASI does not divide the duodenum, thus eliminating the possibility of duodenal stump leakage, a serious complication with an incidence range between; 4) the tension on the anastomosis lower than other techniques; 5) there are no blind loops, excluded segments, or foreign bodies; 6) SASI is completely reversible ⁽¹²⁾.

Single anastomosis sleeve jejunal (SASJ) bypass, which is the focus of this study, is a modification of SASI using a shorter biliopancreatic limb length compared

to SASI to prevent long-term nutritional complications ⁽¹³⁾. The SASJ bypass appears to be safer than the SASI procedure in patients with excessive weight loss and nutritional deficiencies and is simpler due to its improved surgical ergonomics ⁽¹⁴⁾.

Aim of the Work

This study aims to evaluate the three-year outcomes of SASJ bypass as a primary bariatric procedure in a tertiary bariatric center for weight loss, comorbidity resolution, and both early and late complications.

Patients and Methods

Place of the study:

Sohag University Hospitals after approval from the institutional ethical committee.

Type of the study:

Retrospective study with prospective collective data.

Study period:

The study will include all SASJ bypass patients who were operated in sohag university hospitals in the period from January 2019 to june 2023.

Inclusion Criteria:

- Age from 18 to 65 years old.
- Both sexes.
- Body mass index (BMI) > 35 with comorbidities or BMI > 40 with or without comorbidities.
- Primary bariatric procedure.
- Follow up period 2 years or more after SASJ.

Exclusion Criteria:

- Follow up period less than 2 years.
- Previous laparoscopic metabolic surgery
- Patients with huge anterior abdominal wall hernias.
- Cirrhotic patients.
- Pregnant or lactating females.
- Unfit patients for anesthesia.
- patients requiring revisional bariatric surgery.
- Patients with any contraindications to laparoscopic surgery.

Method of the study:

A retrospective study with prospective collected data included a case series of consecutive bariatric patients who underwent SASJ bypass in Sohag university hospitals between the 1st of January 2019 and the 31st of june 2023. The

analysis in the present study included data of all the patients who underwent SASJ as bariatric procedure. All patients were approved as candidates for bariatric surgery by a multidisciplinary screening team, between 18 and 65 years of age and a BMI more than 40 kg/m² or BMI of more than 35 kg/m² combined with comorbidities.

All the required data have been collected from the patients' files at Sohag university hospitals out-patient clinic. To update follow up data for missing patients, a postal questionnaire will be sent to all patients to retrieve the latest outcome. Patients who will not respond will receive a phone call and email if applicable. The postal questionnaire contained questions about:

- a) Current and lowest weight after surgery.
- b) Current comorbidities and medication.
- c) Possible complaints / complications.
- d) Any surgical intervention related to the SASJ bypass.

In case of non-response, the data of the last visit either in hospital or out-patient clinic were used as a final outcome.

Ethical standards:

An oral and written consent will be taken from the patients included in the study and will be introduced to ethics scientific committee at Sohag university hospital for approval.

Preoperative:

As for any bariatric procedure, all patients had a routine preoperative evaluation including history, examination, and laboratory investigations.

If symptomatic GERD was present, an endoscopy was performed. An abdominal ultrasound had been routinely carried out to evaluate the state of the liver and to exclude the presence of gallstones. Low molecular weight heparin had been given subcutaneously for all patients 12 h before surgery as prophylaxis against deep vein thrombosis.

Surgery technique:

The patient had been placed in the French position in a steep reverse Trendelenburg position with the surgeon standing between the patient's legs. All

patients had been operated under general anaesthesia with endotracheal intubation. In the classic sleeve gastrectomy, the operation had been started with the separation of the greater omentum from the stomach. The dissection had been continued upward to dissect the short gastric vessels and to clear the left crus from any attachments. Any adhesion between the stomach and pancreas had been dissected. The dissection had been continued downward till the pyloric ring.

A 36-French calibration tube had been used as a guide for a proper sleeve. Using a linear cutting stapler, stapling had been begun at 6 cm proximal to the pylorus and continued upward to separate the stomach. The staple line has been overseen using a running proline suture 3/0. The sleeve had been routinely fixed to the left crus to prevent pouch migration into the chest and to decrease the reflux.

When the duodenojejunal (DJ) junction is identified, a point 200–250 cm from the DJ had been measured. The intestinal loop had been brought up to the gastric sleeve without dividing the greater omentum and had been fixed with a stay suture to the sleeved stomach at the pyloric ring. A stapled isoperistaltic side-to-side anastomosis had been performed using a forty-five linear cutting stapler at the dissected inferior side of the pylorus. The defect of the gastro-jejunal anastomosis had been closed with a two-layer running suture, and a methylene blue test had been performed to assess for the presence of leaks.

Early ambulation and clear fluids had been started 6 h after surgery. Thrombosis prophylaxis had been continued for 2 weeks, and proton pump inhibitors has been administrated for 4 months postoperatively.

Follow-up:

All patients have been seen in the outpatient clinic weekly for 1, 3,6 and 12 months followed by every 6 months in the second year, and every 6 months in the third year. Patients have been also seen in the clinic if they developed symptoms between their follow-up visits. The minimal follow-up period will be 2 years after the SASJ bypass.

The patients will be evaluated with regard to weight loss and improvement in comorbidities. All patients have been continued on a liquid diet for 2 weeks, followed

by a soft diet in the next week. Subsequently, patients have been put on a high protein, low-calorie diet. Other elements will be introduced sequentially under dietitian supervision. high concentration multivitamin supplements had been prescribed to all patients to be taken regularly for two years then gradually withdrawn, ending with taking only Centrum® in the third year.

Complete blood count including liver function, complete blood panel, HBA1c, fasting blood sugar, serum albumin, serum iron, and serum vitamin D have been performed every three months. The specific investigations have been performed on request according to the patient clinical condition. In addition, any early or delayed complications will be recorded.

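### The two-year follow-up criterion, applied as observed follow-up, drops deaths before 24 months and untraced early losses from the complication, readmission and reoperation rates

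*Protocol*

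**What the plan says.** All places are in the protocol; no SAP is at hand.

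- **Inclusion Criteria:** "Follow up period 2 years or more after SASJ".
- **Exclusion Criteria:** "Follow up period less than 2 years". Neither list makes an exception for death or for early events.
- **Follow-up:** the two-year minimum is repeated, again without saying whether it is elapsed or observed time.
- **Study period:** "The study will include all SASJ bypass patients who were operated in sohag university hospitals" from January 2019 to June 2023. These are operation dates.
- **Method of the study:** the study is described as "a case series of consecutive bariatric patients who underwent SASJ bypass in Sohag university hospitals", and the analysis is said to have "included data of all the patients who underwent SASJ as bariatric procedure". Missing follow-up is to be sought by postal questionnaire, then by phone call and, where applicable, email. After that: "In case of non-response, the data of the last visit either in hospital or out-patient clinic were used as a final outcome". No minimum time is set for that last visit.
- **Aim of the Work:** the procedure is to be evaluated "for weight loss, comorbidity resolution, and both early and late complications".
- **The clinical outcomes, Secondary outcomes:** an early/late split at 30 days, which read with the aim refers to complications, and the rate of readmission and reoperation. No separate denominator is given for any of these.

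**The concern.** A 30-day complication rate describes everyone who had the operation. If entry to the cohort requires that the patient was still under observation two years later, the rate describes only those who survived and stayed in contact. Membership is then decided by post-operative events, some of which are themselves the outcomes or follow from them.

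The plainest case is a patient who dies on day 10. That patient had an early event of the kind the aim asks about, yet cannot have two years of observed follow-up. The eligibility rule removes the patient before any rate is calculated.

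Complications are part of the stated aim, and readmission and reoperation are named secondary outcomes, so the safety half of the report is at stake. The primary weight outcomes are less affected, since a two-year minimum is a relevant choice for them.

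**Working it through.** The protocol states no sample size, event count, expected rate or loss rate, so there is no figure to reproduce. The check is mainly a reading of the text under each meaning of the criterion.

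**Reading A: observed follow-up**

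1. A patient who dies before 24 months has less than two years of follow-up by definition and meets the exclusion criterion. Counted deaths before 24 months = 0, whatever the true number.
2. A patient lost to the clinic before 24 months is excluded unless the questionnaire, phone call or email extends observation past 24 months. Only untraced patients are removed.
3. Those removed take with them any 30-day complication, readmission or reoperation already in their files. Nothing in the protocol keeps them in for early events.
4. Consider a non-responder last seen at 18 months. The last-visit rule would use the 18-month data as the final outcome, while the exclusion criterion removes the patient. The two agree only if the last-visit rule is confined to patients already past 24 months.
5. The result fits poorly with the descriptions of the series as consecutive and as including all SASJ patients.

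**Reading B: time since surgery**

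1. Eligibility depends on operation date alone, so deaths and losses stay in and the selection in Reading A does not arise.
2. The last operations, at the end of June 2023, reach 24 months at the end of June 2025. At any data cut-off from then on, the criterion excludes nobody.
3. The wording on all patients, on consecutive patients and on the last visit then fits without strain.

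**Can the text decide?** The last-visit rule and the words on completeness lean towards B. A minimum follow-up stated per patient in the eligibility lists reads naturally as A. The statement in the Follow-up section fits either.

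**Direction for non-fatal events under Reading A (illustration only; every input is assumed).** Let r be the true event rate, qe the share of patients with an event who lack 24 observed months, and qn the same share among patients without an event. Then

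reported rate = r(1 − qe) / [r(1 − qe) + (1 − r)(1 − qn)].

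With r = 10% and qn = 20%:

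| qe | Calculation | Reported rate |
|---|---|---|
| 10% | 0.09 / (0.09 + 0.72) | 11.1% |
| 20% | 0.08 / (0.08 + 0.72) | 10.0% |
| 40% | 0.06 / (0.06 + 0.72) | 7.7% |
| 60% | 0.04 / (0.04 + 0.72) | 5.3% |

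The reported rate can lie above, at or below the true 10%. It depends on whether patients with complications are lost more or less often than the others. For death before 24 months, qe = 100% and the reported rate is 0%.

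**The case against.** The strongest reply is that the authors meant time since surgery. The operation window closes two years before mid-2025, and the reference list contains 2025 publications, which suggests a window chosen so that everyone could reach two years. The last-visit rule has no minimum time. Listing the criterion twice proves little, since the requirement of a primary procedure is also mirrored among the exclusions. The statement that all patients are included precedes the eligibility lists and can be read as describing the source population. All of this is fair. It makes Reading B plausible, but the intention is inferred and the protocol does not state it.

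A second reply is that tracing can recover patients lost to the clinic. That stands, and it limits the point to deaths and untraced patients.

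A third is that analysis sets belong in the SAP. In part they do. But eligibility is fixed here, and a SAP can restore excluded patients to the safety rates only if their files were extracted. The protocol does not say whether they will be.

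A reader might infer more than the text supports:

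- **That the complication rates will be too low.** The illustration shows that this does not follow for non-fatal events.
- **That the missing data cut-off date is a fault in itself.** It may be set in the SAP.
- **That the share of operations too recent to qualify measures the harm.** Exclusion by date arises under Reading B, where selection on post-operative events does not occur.
- **That the consent rule** ("An oral and written consent will be taken from the patients included in the study") **removes the same patients under either reading.** It is a separate matter and would touch a different group. Someone observed well beyond 24 months may be untraceable now, and someone lost early may later be traced and consent.

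**Conclusion.** The point holds, conditional on Reading A. The criterion is undefined, has no exception for safety outcomes, and can be followed to the letter in a way that yields wrong safety rates. Under observed follow-up, deaths before 24 months cannot be counted; that follows from the wording and needs no assumption about numbers. Untraced early losses also leave both numerator and denominator, with an effect of unknown size and direction on non-fatal events. Under time since surgery the problem disappears.

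It should be fixed, because safety is part of the aim and the remedy is cheap. Confidence is medium, because the authors may have intended the harmless reading.

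**What to change.** 1. Define the cohort as all consecutive primary SASJ operations from January 2019 to June 2023 that meet the preoperative criteria. Remove the follow-up condition from the inclusion and exclusion lists.
2. Use this cohort as the denominator for 30-day complications (including deaths), readmission and reoperation.
3. Report late events with the follow-up available, and give the numbers dead or lost before two years.
4. Apply the two-year minimum only to the weight and comorbidity summaries. State there whether it means time since surgery or observed follow-up, and word the last-visit rule to agree.

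**Cost:** a change of protocol wording and some extra extraction from existing files. The amount is unknown, because the protocol does not say how many patients have under two years of follow-up. Follow-up will look less complete, and the event rates may move in either direction.

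### The questionnaire goes to all patients and last-visit data are the final outcome only on non-response, so, read as written, a self-reported weight can displace a clinic weight

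*Protocol*

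**What the plan says.** The Method of the study section of the Protocol takes the patients' out-patient clinic files as the base source: "All the required data have been collected from the patients" (the sentence goes on to name the files). It then adds a second source: "To update follow up data for missing patients, a postal questionnaire will be sent to all patients to retrieve the latest outcome". The first item on the questionnaire is "Current and lowest weight after surgery"; another asks about present comorbidities and medication. Patients who do not return it are pursued: "Patients who will not respond will receive a phone call and email if applicable". The paragraph closes with its only rule on what counts as the final outcome: "In case of non-response, the data of the last visit either in hospital or out-patient clinic were used as a final outcome".

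The Follow-up section describes clinic contact throughout the period of interest. It says "All patients have been seen in the outpatient clinic" at intervals through the first year, "followed by every 6 months in the second year, and every 6 months in the third year". It also says "The minimal follow-up period will be 2 years after the SASJ bypass", and that patients are evaluated for weight loss and comorbidity improvement.

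The clinical outcomes section calculates %EWL and %TWL from a follow-up weight. It gives neither the source of that weight nor its time point.

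**The concern.** Two sentences in one paragraph do not fit together. The stated purpose limits the questionnaire to patients whose follow-up is missing, while the stated recipients are the whole cohort. If everyone is asked, and visit data become the final outcome when a patient does not answer, then a patient who does answer is represented by the answer. That puts the weaker source ahead of the stronger one for patients who have both.

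The primary outcome is at stake. %EWL and %TWL would mix self-reported weights (responders) with clinic weights (non-responders), taken at uneven times since surgery. If patients report their weight too low, weight loss is overstated. The study is a single-arm descriptive series, so no comparison group could cancel such an error; it goes straight into the reported mean or median. The same order applies to comorbidity status, where a mailed answer could take the place of what the clinic recorded.

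**Working it through.** The Protocol states no figure on this point, so there is none to reproduce. The check is a reading of the text, followed by an illustration of size.

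**Step 1: which source is final for whom, on the wording as it stands**

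| Patient | Clinic weight at year 2 or 3? | Replies? | Final outcome |
|---|---|---|---|
| A | yes | no | last visit (stated) |
| B | no | no | last earlier visit (stated) |
| C | no | yes | self-report (implied) |
| D | yes | yes | self-report (implied) |

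Type D is the problem. If only missing patients were asked, type D would not arise. It arises because all patients are asked and visit data are tied to non-response. Telephone and email replies are also self-report, so pursuing non-responders moves more patients from A to D. No other section gives the clinic value precedence.

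**Step 2: timing**

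The aim is three-year outcomes. Operations ran from January 2019 to June 2023, about 4.5 years. A questionnaire asks for weight on the day it is answered, so time since surgery is set by the reply and not by the visit schedule. The Protocol gives no mailing date, so the actual spread cannot be calculated.

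**Step 3: size per displaced clinic weight (illustration)**

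Assumed inputs, none from the Protocol: under-reporting d = 1 to 3 kg; preoperative weight W = 125 kg; preoperative excess weight E = 55 kg. Preoperative weight and excess weight are the denominators of the Protocol's own formulas, so an error d in the follow-up weight gives:

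- %TWL overstated by 100 × d / W: 100 × 1/125 = 0.8 to 100 × 3/125 = 2.4 points.
- %EWL overstated by 100 × d / E: 100 × 1/55 = 1.8 to 100 × 3/55 = 5.5 points.

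**Step 4: size for the cohort**

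Let f be the share of all patients who are type D. The order of sources shifts the cohort mean by f times the values in Step 3. The Protocol gives nothing from which to derive f. Multiplying by the whole response share would be too much, because type C patients have no clinic weight at that time to displace.

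**Step 5: direction**

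If true weight changes by g kg between the last visit and the reply (positive for regain), the difference from the clinic-based value is 100 × (d − g) / W for %TWL, and likewise with E for %EWL. It is an overstatement when g is less than d and reverses when g exceeds d. The net direction is therefore not established.

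**The case against.** The strongest reply is that the Protocol never says a questionnaire answer replaces a clinic weight. The files are named first as the source, the questionnaire is introduced for missing patients, and the non-response sentence can be read as covering only those patients. On that reading type D does not arise. This stands in part: the override is an inference, and the text supports two readings. But the narrower one has to set aside the plain statement that all patients are asked. Even then, a reported value supersedes the last clinic value for the patients concerned, with no rule on its timing.

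A reader might infer three stronger points that the Protocol does not support:

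- That the questionnaire goes out on one calendar date, fixing a wide spread of follow-up times. No date or single mailing is stated. Uneven timing would also arise with last-visit data alone, since no time point is set for the follow-up weight.
- That self-report replaces a laboratory-defined comorbidity status. The outcome categories are listed but not defined by laboratory values, and the three-monthly blood tests are given without a duration.
- That the cohort mean is inflated by a known amount. Step 4 and Step 5 show why neither the amount nor the sign can be fixed.

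It may also be said that source hierarchy and visit windows belong in a statistical analysis plan, which may exist. That is fair for the details. The point here is narrower: the Protocol itself states the recipients and the fallback rule, and the two do not agree.

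**Conclusion.** The concern holds as a conflict in the Protocol's wording with a probable, not certain, consequence. Followed literally, the Method of the study section makes self-report the final outcome for every responder, including those with a clinic value from the second or third year, at an uncontrolled time since surgery. On the assumed inputs, each displaced clinic weight overstates %TWL by 0.8 to 2.4 points and %EWL by 1.8 to 5.5 points. These figures rest wholly on the assumed 1 to 3 kg, 125 kg and 55 kg, and they describe under-reporting alone. The Follow-up section implies weighing at visits but does not describe it, so how many clinic weights could be displaced is unknown. The point merits correction because the remedy is cheap and gives a better rule than the one stated.

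**What to change.** Reconcile the two sentences in the Method of the study section:

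- Limit the questionnaire's role in the outcome to patients with no clinic weight at the analysis time point (for example 24 and 36 months, with a stated window). It may still go to everyone for other purposes, such as complaints or operations.
- Give clinic-recorded weight and comorbidity data precedence whenever they exist in the window.
- Use a self-reported value, by post, telephone or email, only if it is dated and falls in the window.
- Record the source of each value, report the share that is self-reported, and repeat the primary summary on clinic-recorded values only.

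The precedence rule belongs in the Protocol; the windows and the repeat summary can sit in the statistical analysis plan if there is one. The cost is about two sentences and one source variable in the data set. The downside is that some more recent self-reported values leave the main analysis.
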